3.2 STUDY ACCRUAL STOPPING RULE

Once the 6th participant had reached the 6 months follow up period (or potentially would have reached the 6 months follow-up if the participant died prior to the 6 months follow-up), the study will be halted for a DSMB review of the available data if more than 85% of participants have PD \leq 6 months following the first dosage. In the absence of literature information on response rates with other treatments in the second-line, his threshold comes from the considerations of acceptable response rates used for sample size determination in Section [10.2](#).

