6.3 RESPONSE ASSESSMENT

For the purposes of this study, during the study participants should be re-evaluated for response every 8 weeks (+/- 1 week), according to the [Study Calendar](#).

The Investigator may perform scans in addition to a scheduled trial scan for medical reasons or if the Investigator suspects PD.

Tumor assessments may include the following evaluations: physical examination (with photograph and measurement of skin lesions, as applicable); cross-sectional imaging using computed tomography (CT) or magnetic resonance imaging (MRI) scan of the skull base, neck, chest, abdomen, and pelvis; nuclear bone scan for subjects with known/suspected bone lesions; and CT of the skull base and MRI of brain (at baseline and follow ups as clinically warranted based on symptoms/findings per investigator discretion). The preferred method of disease assessment is CT with contrast. If CT with contrast is contraindicated, CT of the chest without contrast and MRI scan of the skull base, neck, abdomen/pelvis is preferred.

Radiologic imaging: Brain MRI/CT at the baseline and if needed at follow ups. CT scan of skull base, neck, chest, abdomen, and pelvis. or MRI.

In addition, PET (FDG or Dotatate) scan will be acquired at the time of first treatment response evaluation, and at/near radiographic progression, where clinically feasible. PET scan may also be acquired per investigator discretion to characterize metabolic activity of lesions (target/non-target/new) beyond cross-sectional measurement-based response categories, such as in cases of, discordant response among lesions, durable partial response, or other indeterminate radiological changes.

For each participant, the Investigator will designate 1 or more of the following measures of tumor status to follow for determining response: CT or MRI images of primary and / or metastatic tumor masses, physical examination findings, and the results of other assessments.

The measure(s) to be chosen for sequential evaluation during the trial have to correspond to the measures used to document the progressive tumor status that qualifies the subject for enrollment.

Post-baseline response assessments should follow the lesions identified at baseline. The same modality of assessment (e.g., CT) used to identify/evaluate lesions at baseline should be used throughout the course of the study unless subject safety necessitates a change (e.g., allergic reaction to contrast media).

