6.3.6 Progression-Free Survival

PFS is defined as the duration of time from start of treatment to time of progression or death, whichever occurs first.

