10.4.2 Analysis of the Secondary Endpoint(s)

PFS will be determined using the Kaplan-Meier method and will be reported along with 95% confidence intervals. PFS will be defined as the time from the date of first treatment to the date of disease progression or death (any cause) whichever occurs first. Subjects who do not have disease progression or have not died at the end of follow up will be censored at the last known date the subject was progression free.

OS will be evaluated using Kaplan-Meier methods. OS will be defined as the time from the date of first treatment to the date of death (any cause). Subjects who are alive at the end of follow up will be censored at the last known date alive.

Duration of Response: The duration of overall response is measured from the time measurement criteria are met for CR or PR (whichever is first recorded) until the first date that PD or death is objectively documented and is evaluated using the Kaplan-Meier method. Analysis of safety and tolerability is as described in the Section **10.4.3**.

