12.5 RISK/BENEFIT ASSESSMENT

12.5.1 Known Potential Risks

12.5.1.1 Potential Risks Associated with Bintrafusp alfa

Potential adverse reactions attributable to the administration of the study drugs utilized in this trial are discussed in Section [14.1.2](#). Risks include the possible occurrence of any of a range of side effects which are listed in the Consent Document or this protocol document. Frequent monitoring for adverse effects will help to minimize the risks associated with administration of the study agents.

Participants may be harmed from being in this study by toxicity due to the drug or combination of drugs given during this study. M7824 is similar to immune check point inhibitors. There are preliminary data to suggest that not all patients benefit from immune check point inhibitors nor M7824. Additionally, there are preliminary data to suggest that an unexpectedly rapid progression of disease occurs in some patients receiving immunotherapy such as immune checkpoint inhibitors.

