14.1.2 Toxicity

Most of the observed AEs with bintrafusp alfa are similar with class effects of monoclonal antibody blockade of the anti-PD-1/PD-L1 axis, with additional cutaneous side effects presumed to be related to TGF- β signaling modulation. The safety data summarized from April 2020 include data on the pooled expansion cohorts (630 participants): treatment-related (TR) treatment-emergent adverse events (TEAEs) were reported in 426 (67.6%) participants. (47) Most TR

TEAEs were low grade (Grade 1 or 2), while Grade ≥ 3 TR TEAEs occurred in 142 participants (22.5%), and immune related adverse events (irAEs) occurred in 137 (21.7%) participants.

Treatment-related TEAE Leading to Permanent Treatment Discontinuation by System Organ Class and Preferred Term in ≥ 2 participants in the Pooled Analysis of Dose Expansion Cohorts

System Organ Class (SOC) Preferred Term (PT)	EMR200647-001 N = 539 n (%)	MS200647-0008 N = 91 n (%)	Overall N = 630 n (%)
Related TEAE leading to permanent treatment discontinuation	38 (7.1)	12 (13.2)	50 (7.9)
Skin and subcutaneous tissue disorders	11 (2.0)	2 (2.2)	13 (2.1)
Rash maculo-papular	3 (0.6)	1 (1.1)	4 (0.6)
Eczema	1 (0.2)	1 (1.1)	2 (0.3)
Rash	2 (0.4)	0	2 (0.3)
Investigations	6 (1.1)	3 (3.3)	9 (1.4)
Alanine aminotransferase increased	3 (0.6)	1 (1.1)	4 (0.6)
Lipase increased	2 (0.4)	1 (1.1)	3 (0.5)
Aspartate aminotransferase increased	1 (0.2)	1 (1.1)	2 (0.3)
Gamma-glutamyltransferase increased	1 (0.2)	1 (1.1)	2 (0.3)
Gastrointestinal disorders	7 (1.3)	0	7 (1.1)
Colitis	3 (0.6)	0	3 (0.5)
Respiratory, thoracic and mediastinal disorders	5 (0.9)	1 (1.1)	6 (1.0)
Pneumonitis	3 (0.6)	0	3 (0.5)
Dyspnoea	2 (0.4)	0	2 (0.3)
Blood and lymphatic system disorders	4 (0.7)	1 (1.1)	5 (0.8)
Anaemia	1 (0.2)	1 (1.1)	2 (0.3)
Eosinophilia	2 (0.4)	0	2 (0.3)
Renal and urinary disorders	3 (0.6)	0	3 (0.5)
Acute kidney injury	3 (0.6)	0	3 (0.5)
Endocrine disorders	2 (0.4)	0	2 (0.3)
Adrenal insufficiency	2 (0.4)	0	2 (0.3)

Source: ADAE 30OCT2018 12:04 Outputid: t31.doc.

TEAEs leading to death occurred in 79 (12.5%) participants with similar rates in EMR200647-001 and MS200647-0008; 7 deaths were due to treatment-related TEAE: 1 participant had dyspnea, hemolysis and thrombocytopenia, 1 participant had an intracranial tumor hemorrhage, 1 participant had pneumonia, 2 participants died of interstitial lung disease, 1 participant due to sudden death, and 1 due to septic shock.

Common TEAEs (occurring in more than 10% of participants) were:

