17.3 APPENDIX C: BEST OVERALL RESPONSE PER RECIST 1.1

RECIST version 1.1 will be used in this study for assessment of tumor response.(1)

For Participants with Measurable Disease (i.e., Target Disease)

Target Lesions	Non-Target Lesions	New Lesions	Overall Response	Best Overall Response when Confirmation is Required*
CR	CR	No	CR	≥ 4 wks. Confirmation**
CR	Non-CR/Non-PD	No	PR	≥ 4 wks. Confirmation**
CR	Not evaluated	No	PR	
PR	Non-CR/Non-PD/not evaluated	No	PR	
SD	Non-CR/Non-PD/not evaluated	No	SD	Documented at least once ≥ 4 wks. from baseline**
PD	Any	Yes or No	PD	no prior SD, PR or CR
Any	PD***	Yes or No	PD	
Any	Any	Yes	PD	

* See RECIST 1.1 manuscript for further details on what is evidence of a new lesion.
 
** Only for non-randomized trials with response as primary endpoint.
 
*** In exceptional circumstances, unequivocal progression in non-target lesions may be accepted as disease progression.
 
Note: Participants with a global deterioration of health status requiring discontinuation of treatment without objective evidence of disease progression at that time should be reported as “symptomatic deterioration.” Every effort should be made to document the objective progression even after discontinuation of treatment.
				

For Participants with Non-Measurable Disease (i.e., Non-Target Disease)

Non-Target Lesions	New Lesions	Overall Response
CR	No	CR
Non-CR/non-PD	No	Non-CR/non-PD*
Not all evaluated	No	not evaluated
Unequivocal PD	Yes or No	PD
Any	Yes	PD

* 'Non-CR/non-PD' is preferred over 'stable disease' for non-target disease since SD is increasingly used as an endpoint for assessment of efficacy in some trials so to assign this category when no lesions can be measured is not advised

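### The accrual halt in Section 3.2 counts progression but not death, so one death without PD among the first six blocks the trigger at a single look, or delays it if the rule is checked repeatedly

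*Combined protocol and SAP*

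**What the plan says.** Section 3.2 places the look when the sixth participant reaches 6 months of follow-up or, in case of an earlier death, when he or she "potentially would have reached the 6 months follow-up if the participant died prior to the 6 months follow-up". At that point "the study will be halted for a DSMB review of the available data if more than 85% of participants have PD" within 6 months of the first dose. The section attributes the threshold to the response rates considered in Section 10.2.

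Sections 6.3.3.1 and 6.3.3.2 define PD by lesion growth or new lesions. Death is not part of that definition, and no other section counts death as PD for this rule. Section 7.4.2 points back to 3.2 for the halting criteria and adds no definition.

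Elsewhere the plan counts death explicitly. Section 6.3.6 reads "PFS is defined as the duration of time from start of treatment to time of progression or death, whichever occurs first". Section 10.4.2 gives PFS as "the time from the date of first treatment to the date of disease progression or death (any cause) whichever occurs first", and it ends duration of response at PD or death.

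Section 3.2 does not say whether the rule is checked once or again after each later participant. It also does not say whether checkpoint-naïve (CN) participants, checkpoint-resistant (CR) participants or both form the denominator.

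**The concern.** The timing clause keeps a participant who has died among the six. That participant stays in the denominator but, without PD, cannot enter the numerator. A death without PD therefore has the same weight as a participant who is alive and free of progression.

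This also does not fit the stated source of the threshold. On a response scale a death without response is a non-response. At most, Section 10.3.2 would take a participant who was never rescanned out of the evaluable set. In neither case does the death count in the drug's favour.

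The plan itself makes such deaths foreseeable. The first scheduled scan is at 8 weeks ("participants should be re-evaluated for response every 8 weeks"). Section 12.5.1.1 warns that "unexpectedly rapid progression of disease occurs in some patients receiving immunotherapy such as immune checkpoint inhibitors". Section 14.1.2 reports that, among 630 participants in pooled cohorts, "7 deaths were due to treatment-related TEAE". At stake is whether the early automatic pause works when it is most needed.

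**Working it through.** **Inputs.** The threshold (strictly above 85%), the six participants and the 6 months come from Section 3.2. Accrual of 6 to 8 participants per year and the 0/12 stage-1 stop come from Section 10.2. Two quantities are not in the documents and are assumed:
- f, the probability of PD or death by 6 months: 80% or 90%.
- s, the share of failures that are deaths without PD: 1%, 5% or 10%.

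Participants are treated as independent.

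**1. The plan's own figure.** Section 3.2 gives no trigger count or operating characteristic. The design that it relies on does: the probability of early termination at a 5% response rate is 0.95^12 = 0.5404, which matches the 54.0% in Section 10.2. The final boundary of 3/21 = 14.3% leaves 18/21 = 85.7% without response, close to 85%. That this is the origin of the threshold is an inference.

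**2. Trigger at six.** 5/6 = 83.3% does not exceed 85%; 6/6 = 100% does. So no non-event is tolerated.
- Five PDs plus one death without PD: 5/6 = 83.3%, silent.
- Four PDs plus two such deaths: 4/6 = 66.7%, silent.
- If death counts, both are 6/6 and trigger.

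**3. Single look.** Given that all six fail, the rule is silent with probability 1 − (1 − s)^6. The joint probability that all six fail and the rule is silent is f^6 × [1 − (1 − s)^6], with 0.8^6 = 0.2621 and 0.9^6 = 0.5314.

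| s | Silent, given all six fail | Joint, f = 80% | Joint, f = 90% |
|---|---|---|---|
| 1% | 5.9% | 1.5% | 3.1% |
| 5% | 26.5% | 6.9% | 14.1% |
| 10% | 46.9% | 12.3% | 24.9% |

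**4. Running check.** One non-event is tolerated from seven participants on (6/7 = 85.7%). Two are not tolerated at 13 (11/13 = 84.6%) and first pass at 14 (12/14 = 85.7%). Given that all fail, the rule has fired by the 13th participant exactly when at most one of the first seven is a death without PD. That probability is (1 − s)^7 + 7s(1 − s)^6 = 99.8%, 95.6% and 85.0%, so the rule is silent with probability 0.2%, 4.4% and 15.0%.

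One extra participant takes 12/8 to 12/6 = 1.5 to 2 months, if that participant has PD. Eight extra participants (from 6 to 14) take 12 to 16 months, if all eight have PD.

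**5. Does the stage-1 interim come before the 14th participant's 6-month point?** Section 10.4.5 halts CN enrolment after the first restaging scan of the last evaluable participant needed, and sends the report to the DSMB. Suppose that both deaths are inevaluable under Section 10.3.2 and are replaced. The 12th evaluable participant is then the 14th treated, and that participant's 8-week scan falls about 4 months before the 6-month point. With a CN-only denominator and no responses, the interim comes first.

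**The case against.** **The wording fits a running rule.** It sets a starting point rather than a single date, Section 7.4.2 has the DSMB meet when the criteria are met, and a percentage is an odd way to write six out of six. This stands as a possible reading. It turns a missed trigger into a delayed one; it does not make death count.

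**The gap is narrow.** Section 3.2 does not ask for documented PD. Section 3.9.1 recognises clinical progression, and Section 8.4 refers to death due to disease progression. Section 3.7 continues scans after treatment, Section 6.3 allows extra scans when PD is suspected, and Appendix C says "Every effort should be made to document the objective progression even after discontinuation of treatment". These provisions do reduce the number of affected deaths. But Section 3.9.1 governs removal from therapy, and Appendix C labels deterioration without objective evidence as symptomatic deterioration, not PD. None of them reaches a toxic death, and none ensures that a death before the first scan is counted.

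**Other safeguards act faster.** SAEs go to the sponsor within 24 hours (Section 8.3). Certain deaths within 30 days, other than those from progressive disease, are reported within one business day (Section 7.3). The team meets about weekly (Section 7.4.1), and the study can be suspended or stopped for safety (Sections 3.9.4 and 13.1). The DSMB reviews at least annually or on request. Six participants take 9 to 12 months to accrue; with 6 months of follow-up the look falls at about 15 to 18 months, so an annual review would already have been due. This stands and limits the consequence.

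**The look schedule matters more.** At f = 90% with deaths counted, moving from a single look to a running check through 13 participants raises the trigger probability from 53.1% to 85.0%. That is more than counting deaths adds to a single look at any assumed s. This also stands, and the fix covers it. But an unstated schedule or denominator is missing detail and would not carry the point alone.

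**Two stronger readings are tempting.** A reader might infer a delay of 12 to 16 months from the 12/14 figure. The documents support that only if a participant responded or if CR participants are in the denominator; otherwise the stage-1 interim intervenes. A reader might also take 7/630 as the rate of deaths without PD. Section 14.1.2 does not split those deaths by prior progression, so it shows only that treatment-related deaths occur.

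**Conclusion.** The point holds on the wording of Section 3.2: death dates the look but is not a failure. Because six participants leave no slack, one death without PD is enough to keep the rule silent when the other five have all progressed. A missed automatic review requires the single-look reading. On the running reading, one such death costs about 1.5 to 2 months.

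The probability that all six fail and a single look is silent ranges from 1.5% to 24.9% over the assumed values of s and f. The documents give neither quantity, so this range illustrates the size and does not estimate it.

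A reader might conclude that the trial could continue unchecked after every participant has failed. The documents do not support that: the loss is one automatic pause for review, and the other reporting routes, DSMB reviews and the 0/12 stop remain. The rule should still be corrected, because followed as written it gives the wrong answer in the case it was built for.

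**What to change.** In Section 3.2, define the event as PD or death from any cause within 6 months of the first dose, in line with Sections 6.3.6 and 10.4.2. In the same sentence, state:
- that the denominator is participants who have reached, or would have reached, 6 months of follow-up;
- which cohort or cohorts count;
- whether the rule is checked once at the sixth participant or again after each later one.

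The change is to protocol wording only. Its cost is that the DSMB review is triggered somewhat more often. At an assumed 90% failure rate, the single-look trigger probability becomes 0.9^6 = 53.1%, instead of [0.9(1 − s)]^6 = 50.0%, 39.1% or 28.2% for s = 1%, 5% or 10%. For a running check through 13 participants, let q be the probability that a participant counts as an event. The formula q^7 + 7q^6(1 − q) gives 85.0% with q = 0.9, instead of 82.8%, 73.1% or 60.4% with q = 0.9(1 − s). What is triggered is a review, not termination.

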3.3 DRUG ADMINISTRATION

3.3.1 Dosage of bintrafusp alfa

Participants will receive bintrafusp alfa 1,200mg IV over 60 minutes (+/- 20 minutes) once every 2 weeks. Bintrafusp alfa will be administered as a flat dose of 1,200 mg independent of body weight (starting dose and all subsequent dose administrations).

3.3.2 Preparation of bintrafusp alfa

Visually inspect the vial for particulate matter and discoloration. Bintrafusp alfa is a clear, colorless to slightly yellow solution. Discard the vial if the solution is cloudy, discolored, or contains particulate matter. Further dilute the bintrafusp alfa in 0.9% sodium chloride to a final concentration between 0.16 mg/mL to 9.6 mg/mL. Gently invert the bag to mix the diluted solution and avoid foaming or excessive shearing. Inspect the solution to ensure it is clear, colorless, and free of visible particles. Discard any partially used or empty vials.

3.3.3 Administration of bintrafusp alfa

Infusion: Administer the diluted solution via IV infusion with a mandatory 0.2 micron in-line filter over 60 minutes. Infusions may be done peripherally or via central venous access device (not required by study). Prior to infusion via port, the primary port material must be an approved material as indicated in “PowerPort Material Analysis for M7824 Administration,” a CCR pharmacy document. Do not co-administer other drugs through the same intravenous line. After administration, a flush of the line with 0.9% NaCl is recommended but not mandatory.

Please refer to [Appendix B](#) for administration rates following an infusion-related reaction.

Premedication: To mitigate potential infusion-related reactions, premedication with an antihistamine and with acetaminophen (for example, 25-50 mg diphenhydramine and/or 500-650 mg acetaminophen) within approximately 30 to 60 minutes prior to the infusion of bintrafusp alfa is optional and at the discretion of the investigator. The premedication regimen may be modified per local site procedures and based on participant-specific factors.

For prophylaxis of flu-like symptoms, a NSAID, for example, ibuprofen 400 mg or comparable NSAID dose, may be administered 2 hours before and 8 hours after the start of each dose of bintrafusp alfa IV infusion, in participants without contraindications to NSAIDs (including allergy to class, renal function impairment, concurrent glucocorticoids).

Setting: Bintrafusp alfa should be administered in a setting that allows for immediate access to an intensive care unit or equivalent environment and administration of therapy for anaphylaxis, such as the ability to implement immediate resuscitation measures. Glucocorticoids (dexamethasone 10 mg), epinephrine (1:1,000 dilution), allergy medications (IV antihistamines), bronchodilators, or equivalents, and oxygen should be available for immediate access.

NOTE: Treatment with bintrafusp alfa is planned to be administered on an outpatient basis. At the discretion of the investigator (e.g., for additional monitoring, participant social reasons, scheduling logistics, etc.), participants may be treated on an inpatient basis. Any such cases of **elective hospital admission** are not considered reportable serious adverse events per Section [8.1.2](#).

Observation period: Participants must be monitored for infusion-related reactions after bintrafusp alfa infusions for a minimum of 30 minutes for the first 4 infusions and as clinically indicated thereafter.

Reported adverse events and potential risks are described in Section [14.1.2](#). Participants will be encouraged to report any and all adverse events.

3.4 DOSE MODIFICATIONS

3.4.1 Discontinuation

Treatment with bintrafusp alfa will be discontinued in participants experiencing specific adverse events; subjects will remain on study for follow up of survival. Treatment will be discontinued in any participant in the case of:

- Any Grade 4 or higher adverse drug reactions (ADRs) graded according to NCI CTCAE v5.0 and assessed as possibly related to that agent by the Investigator, except for laboratory values that are asymptomatic or resolve to Grade ≤ 1 or baseline grade within 7 days without medical intervention.

- Any Grade 3 ADRs possibly attributed to any agent **except** for any of the following:
 - Transient (\leq 48 hours) Grade 3 nausea and vomiting, headache, flu-like symptoms, fever, controlled with appropriate medical management.
 - Tumor flare phenomenon defined as local pain, irritation, or rash localized at sites of known or suspected tumor.
 - Endocrinopathy that can be medically managed with hormone replacement.
 - Keratoacanthoma and squamous cell carcinoma of the skin. Suspicious skin lesions will be evaluated by dermatology and managed per recommendations (**Appendix B**: Recommendations for Management of IRRs and AEs, Table C), including potential removal of the lesion.
 - Grade 3 laboratory test abnormalities that resolve to Grade \leq 1 or to baseline Grade within 7 days with appropriate medical management or Grade 3 laboratory test abnormalities that are determined not to be clinically significant or asymptomatic.
 - Grade 3 anemia with Hgb <8.0 g/dL that is clinically manageable with PRBC transfusions does not require treatment discontinuation.
 - Any Grade 3 ADR which in the opinion of the investigator is not clinically relevant or can be managed with minimal risk to the participant (e.g. placement of a pleural catheter for recurrent inflammatory pleural effusions).

